10.1.3 Formulation and Packaging

Favipiravir will be provided to the study team from the manufacturer (Avigan®; FUJIFILM Toyama Chemical Co., Ltd) via Appili Therapeutics. The medication is supplied as tablets and is orally administered. Appili will supply placebo tablets of similar but not identical appearance, with a formulation equivalent to the active product, minus the active pharmaceutical ingredient.

Favipiravir can be crushed for persons unable to swallow tablets. If necessary, nurses at the bedside will crush favipiravir or placebo tablets immediately before administration and disperse them in water, cranberry juice or apple sauce for administration to residents either orally or by feeding tube (for residents who have pre-existing chronic feeding tubes) who cannot swallow tablets.

Details of the chemical composition and appearance are provided below in Table 1. Favipiravir will be provided in blister packs. All study products (Favipiravir and placebo) will be labeled as Investigational Product in accordance with Health Canada regulations.

Table 1. Formulation, Appearance and Composition of Favipiravir®

	Avigan®		
	Tablet		
Formulation	C5H4FN3O2; favipiravir		
DIN			
Appearance	Light yellow round tablet 8.7 mm in		
	diameter		
Non-	Colloidal silicon dioxide (diluent),		
medicinal	povidone K30 (binder), low-		
ingredients	substituted hydroxypropyl cellulose		
	(disintegrant), crospovidone		
	(disintegrant), and sodium stearyl		
	fumarate (lubricant). Film coated with		
	OPADRY, which includes		
	Hypromellose (2910, 6mPas), titanium		
	dioxide, talc, and yellow ferric oxide.		

10.1.4 Storage and Stability

Favipiravir is a novel nucleic acid (pyrazine molecule) analogue that interferes with viral ribonucleic acid (RNA) replication. Favipiravir is supplied as a light yellow, film-coated tablet for oral administration containing 200 mg favipiravir. Favipiravir tablets are to be kept in a dry area, stored at 15° C to 30° C and shielded from direct light.

10.1.5 Study Drug Dispensation

For residents, study drug will be provided from a research pharmacy to the dispensing pharmacy for each enrolled LTCH. The dispensing pharmacy will be responsible for packaging and arranging transportation of medications to each LTCH. The medications will then be dispensed to each enrolled resident by the LTCH nursing staff as per routine medication administration processes.

For LTCH staff, the medication will be dispensed from the research pharmacy to research coordinators who will be responsible for arranging transportation to the study participants and documenting this process.

10.1.6 Expected Side Effects

Favipiravir is considered a safe drug. No treatment related serious adverse events occurred in licensure studies of favipiravir. The most common adverse events observed in clinical trials are gastrointestinal (diarrhea 2.3%; nausea 2.1%). A similar proportion of subjects in the placebo (25.4%) and favipiravir (25.3%) groups experienced at least 1 adverse event. Further favipiravir is associated with increased uric acid level which are typically asymptomatic and would be expected to be transient with the duration of treatment to be used in this trial.

10.1.7 Additional Safety Considerations

For the purpose of this trial, the following are exclusion criteria for study drug administration:

- 1. Pregnancy
- 2. History of abnormalities of uric acid metabolism, other than gout.
- 3. Subject has a history of hypersensitivity to remdesivir or favipiravir
- 4. Known hepatic cirrhosis
- 5. Current use of the following medications, which cannot be discontinued for the duration of the study: pyrazinamide, hydralazine, more than 3000 mg of acetaminophen per day.

The following safety considerations are based on data from individuals taking favipiravir for influenza. They are listed here for reference.

- *Phototoxicity*: Nonclinical studies have shown mild phototoxicity. One study subject experienced mild photosensitivity (rash) following a tanning bed session. All subjects should avoid excessive exposure to sunlight or artificial ultraviolet light.
- *Laboratory Values*: Mild to moderate asymptomatic elevations of uric acid and aminotransferase have been observed in healthy volunteers and subjects with influenza treated with favipiravir in clinical studies. The changes have been reversible upon favipiravir discontinuation.
- *Mutagenesis:* Favipiravir proved mildly positive under some conditions studied in the mammalian chromosomal aberration test and mouse lymphoma assays at high concentrations. Although the potential for genotoxicity at high exposures cannot be ruled

- out, evidence indicates that this risk is minimal at the exposures planned in this clinical study.
- GI Tract Lesions: In two proof-of-concept studies of orally administered favipiravir against Ebola virus infection in macaques, GI tract lesions were observed that were not consistent with the known natural history of Ebola nor with previous animal and clinical studies of favipiravir. However, evidence suggests that bacterial infections and preexisting enterocolitis in the treated macaques may have been responsible, and an ongoing risk to patients may not exist.

10.1.8 Concomitant and Prohibited Medications

There are no absolute contraindications for using favipiravir with other medications. However, numerous precautions exist. Favipiravir clearance may be reduced in the setting of aldehyde oxidase inhibitors and may increase the plasma concentration of aldehyde oxidase substrates. For the safety of residents, current receipt of the following medications which may have interactions with favipiravir will result in residents not receiving study drug if they cannot be discontinued for the duration of the study: pyrazinamide, hydralazine, more than 3000 mg of acetaminophen per day.

10.2 Control

The comparator arm in this trial will be placebo. No existing pharmacologic agents have been demonstrated to have confirmed clinical activity against COVID-19; some agents have invitro activity against SARS-CoV-2 and may have potential benefit in observational studies. In the absence of confirmed evidence for benefit or harm of active pharmacologic agents for treatment or prophylaxis of COVID-19, the use of a placebo is justified.

10.3 Co-Intervention(s)

LTCHs in both arms will implement standard infection prevention and control measures for COVID-19 outbreaks, including case-isolation, visitation limitation, cancellation of activities, handwashing, and use of personal protective equipment per Ministry of Health and Long-Term Care mandates, and in collaboration with their local Public Health Unit, and infection prevention and control from any hospital who is working with the LTCH.

10.4 Participant Access to Study Medication at Study Closure

This study will provide access to the study drug for those randomized to the intervention arm only. In the event that a study participant tests positive for COVID-19 during the follow-up period, efforts will be made to link the individual to ongoing clinical trials of COVID-19 treatment if such trials are enrolling in proximity to the LTCH unit. However, no guarantees of access to investigational product can be made. At the time of writing, there are no known effective treatments for established COVID-19 infection.

11. RISK MANAGEMENT

11.1 Pregnancy

Favipiravir is contraindicated in pregnancy. If a participant becomes pregnant during the study, the Investigator must inform the Sponsor and the study drug will be discontinued. Follow-

up should be continued until study close-out at the study centre. Pregnancy is not an adverse event; however, any complication related to pregnancy should be considered an adverse event.

11.2 Protection of Study Personnel from COVID-19

COVID-19 is transmitted from person-to-person through respiratory droplets and via fomites. While the greatest risk of transmission is believed to occur in the context of respiratory symptoms, transmission from asymptomatic and minimally symptomatic individuals may occur. Participants in this trial will all have been recently exposed to a confirmed case of COVID-19 disease and will thus be at increased risk of having early or incubating infection during the incubation period. They are also residing in a group setting for vulnerable adults, such that introduction of the virus by asymptomatic study personnel is an important risk. For these reasons, several measures will be taken to minimize the risk of transmission to both study personnel and residents.

Where possible, communication with residents and LTCH staff, and in-person visits to LTCHs will be virtual. When study personnel conduct in-person visits during the outbreak, a surgical mask should be placed on the participant if possible, and droplet precautions will be used by LTCH staff during the study visit, including surgical mask, face shield or goggles, disposable gown, and gloves. After the outbreak has been deemed terminated, further visits can be conducted using routine precautions. All study personnel will be excluded from work if they develop a fever or any respiratory symptoms, and will follow public health guidelines regarding any visits to LTCHs. Any study personnel who develop symptoms potentially suggestive of COVID-19 disease will immediately be assessed by occupational health and relieved of study duties until deemed safe to return to work. Study personnel will comply with all requests from public health units related to study visits, practices in the LTCH and submission of swabs for COVID-19 testing.

12. CLINICAL AND LABORATORY EVALUATIONS

12.1 Clinical Evaluations

Once consent is obtained, data on patient underlying illness and medications will be obtained from LTCH medical records and residents/substitute decision makers.

For the study period, daily line lists of new symptoms in residents, and of those who have had specimens sent for COVID-19 testing will be recorded and faxed to the study office. All results of COVID-19 testing, whether in the nursing home or after hospital admission, will be obtained and recorded for the study. The identifying information on this line list is the names of residents. LTCH staff will black out the names of residents not participating in the study before faxing the line list to the study office. The line list will be sent to a secure fax in a locked office at Sinai Health System, where study codes will be immediately applied and resident names blacked out.

Any residents who develop adverse events, and any calls for physician assessment will also be recorded on the line lists. The study will contact physicians to identify the result of their assessment of the resident to determine whether COVID-19 is a possible diagnosis, or whether an adverse effect has occurred. Where possible, study staff will review electronic records of nursing notes daily.

Data will be recorded onto standardized electronic case report forms hosted on secure servers at the Applied Health Research Centre (AHRC) at St. Michael's Hospital.

12.2 Laboratory Evaluations and Specimen Collection

12.2.1 Microbiologic testing for SARS-CoV-2

It is expected that all residents or staff who meet the case definition for COVID-19 will have specimens obtained clinically for testing, the results from which will be recorded. However, if any such cases do not meet criteria for clinical testing, specimens will be submitted to the study laboratory for testing in real time. Any resident who dies in the home during the study period will have a nasopharyngeal swab submitted for COVID-19 testing.

At baseline (day 0) and on day 14 and day 40, participants will undergo collection of nasopharyngeal or nasal swab for RT-PCR testing. Testing will be performed using licensed tests for COVID-19 by research laboratories licensed to perform such tests.

12.3 Questionnaires

See Appendix for questionnaires and data collection forms.

12.4 Stored Research Specimens and Plans for Possible Future Testing

Any respiratory specimens collected from participants for solely study purposes will be stored until no longer needed by the study, then discarded.

13. STUDY PROCEDURES

13.1 Schedule of Events

To protect study and long-term care home staff, residents and substitute decision makers, all efforts will be made to have any contacts be virtual. Where possible, consent will be obtained by telephone or video link, and data will be obtained by telephone, fax, or remote data entry.

13.2 Screening, consenting and initial data collection Visit

The purpose is to rapidly assess participant eligibility and obtain written informed or preliminary verbal consent to participate in the trial, as eligibility and consent are required from at least 80% of residents on the outbreak ward in order to randomize. A nasopharyngeal or nasal swab will be obtained from all residents on day 0, and from all staff as soon as practical.

The study coordinator will:

- Review the patient's chart and medication record to assess eligibility; if possible, this will be performed remotely either via research staff having access to electronic charts, or by having a staff member in the home transmit the information by telephone or fax.
- If written informed consent has not yet been obtained, provide and review the informed consent document via email / fax / telephone / video link with each resident, substitute decision maker or staff person, and obtain and document verbal consent to participate.
- Advise the participant/substitute decision maker that written consent will be required as soon as possible and agree on the method by which this will be done.
- Provide contact information for the study, such that each participant has access to study personnel at any time to answer questions
- Obtain multiple forms of contact information for consenting participants, including multiple telephone numbers, an email address, and a mailing address for study material delivery.
- For study staff:
 - o Complete the baseline interview for study staff.
 - o Decide whether staff will complete daily diaries online or on paper
 - Review with the participant how to access and complete the symptom/adherence diary and questionnaires, and encourage immediate completion of the baseline questionnaire on the day of the visit.

13.3 Medical Oversight

Confirmation of eligibility, assessment of adherence of study drug/placebo, evaluation of overall participant safety, review/assessment of minor and/or serious adverse events (including classification of adverse events according to seriousness, severity, relatedness and expectedness), and final sign off of data collection will be done by the qualified investigator/principal investigator ([name]) or a medically qualified and licensed delegated physician.

Table 1. Schedule of Events for Residents

Visit	Screening (Day 0)	Baseline (Day 1)	Day 14±2d	Day 40±4d	Day 60±7d
Visit format	Remote	Remote	In person	In person	Remote or
					in person
Eligibility	X				
assessment					
Informed consent	X				
Cluster		X			
randomization					
Dispensing study		X			
drugs					
Assessment for		Daily, by LT	ΓC staff (fax to	study)	
COVID-19		Chart review by	study staff, da	ay 14 & 40	
Concomitant medi-	X		X	X	
cation assessment					
Adverse event		Daily by LT	C staff (fax to	study)	SAE only
assessment		Chart review by study staff, day 14 & 40			
Death/hospital		Daily by LTC staff (fax to study)			X
transfer document.		Chart review by study staff, day 14 & 40			
Nasopharyngeal/	X		X	X	
nasal swab					
Medication			X	X	
adherence					

Table 2. Schedule of Events for Staff

Visit	Screening (Day 0)	Baseline (Day 1)	Day 14±2d	Day 40±4d		
Visit format	Remote or	Remote	Remote or in person	In person		
	in person*					
Eligibility	X					
assessment						
Informed consent	X					
Cluster		X				
randomization						
Dispensing study		X				
drugs						
Interview by study	X		X	X		
staff						
Concomitant medi-	X		X	X		
cation assessment						
Adverse event			X	X		
assessment						
Daily diary		Daily symptom/adverse event/adherence diary to be completed				
Visit-specific	X		X	X		
questionnaire						
Nasopharyngeal/	X^1		X	X		
nasal swab						
Pill count				X		

^{*}If staff are willing and able to do their own nasal swab, then visits will be remote. Consents and questionnaires will be returned by mail or fax, or collected at the LTCH. Pill bottles will be returned to a secure location at each LTCH to be collected by study staff.

¹For staff, nasopharyngeal/nasal swabs may be obtained on day 0-3, as they may not be obtained until the first time that the staff member attends at the LTCH to complete a shift. New staff starting work during the outbreak will be requested to have a swab on the first day that they work.

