Duration of Treatment	Starting once a COVID-19 outbreak in an LTCH unit (>=2 symptomatic microbiologically confirmed COVID-19 cases) has been identified and continuing until day 25		
Outcome Measures	Primary outcome:		
	Control of outbreak, defined as no new cases of COVID-19 in residents for 24 consecutive days up to day 40 after the		

	start of prophylaxis
	Secondary outcomes:
	1. The proportion of residents of included LTCH units who die up to day 40, and up to day 60
	2. The proportion of residents of included LTCH units who were uninfected at baseline and develop new symptomatic microbiologically confirmed COVID-19 up to day 40
	3. The proportion of exposed staff uninfected at baseline in whom SARS-CoV-2 infection is identified up to day 14 and up to day 40
	4. The proportion of residents of included LTCH units hospitalized up to day 40
	5. The proportion of residents of included LTCH units who discontinue study medication due to adverse events
	6. The proportion of LTCH staff of included LTCH units who discontinue study medication due to adverse events.
	7. The occurrence of new microbiologically confirmed COVID-19 infections in residents in other units of the facility up to day 40 (dichotomous, at LTCH level)
	8. The proportion of previously unaffected LTCH units of the remainder of the facility in which a case of COVID-19 is identified
	9. The proportion of residents in the remainder of the facility who develop COVID-19 infections up to day 40
Statistical Analysis	Primary outcome: Fisher's exact test (two-sided) comparing control of outbreak in homes receiving study drug versus placebo

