6.4 Endpoint Assessment

The primary outcome (primary endpoint) will be control of outbreak, defined as no new cases of COVID-19 in residents for 24 consecutive days up to day 40 after the start of prophylaxis. This outcome is dichotomous (yes/no) and will be determined at the level of the cluster (LTCH unit).

Secondary outcome measures (endpoints) are:

- 1. The proportion of residents of included LTCH units who die up to day 40, and up to day 60
- 2. The proportion of residents of included LTCH units who were uninfected at baseline and develop new symptomatic microbiologically confirmed COVID-19 up to day 40
- 3. The proportion of exposed staff uninfected at baseline in whom SARS-CoV-2 infection is identified up to day 14 and up to day 40
- 4. The proportion of residents of included LTCH units hospitalized up to day 40
- 5. The proportion of residents of included LTCH units who discontinue study medication due to adverse events
- 6. The proportion of LTCH staff of included LTCH units who discontinue study medication due to adverse events.
- 7. The occurrence of new microbiologically confirmed COVID-19 infections in residents in other units of the facility up to day 40 (dichotomous, at LTCH level)
- 8. The proportion of previously unaffected LTCH units of the remainder of the facility in which a case of COVID-19 is identified
- 9. The proportion of residents in the remainder of the facility who develop COVID-19 infections up to day 40

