13.6 Day 60 Visit

At the day 60 visit assessment includes, by telephone from the LTCH or by in person visit:

- SAEs, hospitalizations, deaths for residents
- Number of microbiologically confirmed COVID-19 cases that have been identified in staff and residents to day 60.

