14.1.2 Serious Adverse Events (SAEs)

A SAE is defined as an AE meeting one of the following criteria at any dose:

- Results in death during the period of protocol-defined surveillance
- Is a life-threatening event (defined as a participant at immediate risk of death at the time of the event)
- Results in in-patient hospitalization or prolongation of existing hospitalization during the period of protocol-defined surveillance
- Results in persistent or significant disability or incapacity (disability is defined as a substantial disruption of a person's ability to conduct normal life functions)
- Is a congenital anomaly or birth defect

Any other important medical event that may not result in one of the above outcomes, may be considered a SAE when, based upon appropriate medical judgment, the event may jeopardize the participant and may require medical or surgical intervention to prevent one of the outcomes listed above. Examples of such medical events include allergic bronchospasm requiring intensive treatment in an emergency room or at home, blood dyscrasias or convulsions that do not result in in-patient hospitalization, or the development of drug dependency or drug abuse.

Participants will be monitored during the 60-day study period for SAEs. If an SAE is ongoing at the time a participant discontinues/completes the study, the SAE will be followed until the Investigator agrees that the event is satisfactorily resolved, becomes chronic, or that no further follow-up is required.

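### The resident day-60 contact may be made as early as day 53, so deaths and serious adverse events in the last week of the 60-day horizon can go unasked about

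*Protocol*

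**What the plan says.** Section 6.4 lists as the first secondary outcome "The proportion of residents of included LTCH units who die up to day 40, and up to day 60". The horizon is a fixed day, with no tolerance around it.

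Table 1 in Section 13.3 (Medical Oversight) gives the resident visits as "Visit Screening (Day 0) Baseline (Day 1) Day 14±2d Day 40±4d Day 60±7d". In the row for deaths and hospital transfers, home staff report daily, with chart review at days 14 and 40. Under day 60 there is a single mark. In the adverse-event row the day-60 column is limited to serious events.

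Section 13.6 describes that last contact as one telephone call or one visit, covering "SAEs, hospitalizations, deaths for residents" and a count of confirmed cases in staff and residents to day 60.

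Two safety sections bear on when capture stops. Section 14.1.2 says "Participants will be monitored during the 60-day study period for SAEs". Section 14.3 records adverse events from randomization until the participant leaves the study at the end of the last visit, or earlier on discontinuation. Section 14.2 requires serious events to be reported within 24 hours of the site learning of them.

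**The concern.** The endpoint closes on day 60, but the contact that informs it may be made a week before. A call on day 53 is fully compliant and cannot report a death on days 54 to 60. Nothing in the protocol asks for a second check when the contact is early.

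At stake is the completeness of day-60 mortality, a named secondary outcome, and of the 60-day serious-adverse-event count, a safety outcome in Section 15.3.2. If one contact date serves a whole unit, the shortfall applies to every resident of that unit at once. With 8 units per arm, differences in scheduling need not even out between arms. An analysis plan can set rules for assigning events to days, but it cannot recover deaths that nobody asked about.

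**Working it through.** The plan gives no figure for this point. Its power statement (above 85% for 8 units per arm, 12.5% against 87.5% control, two-sided Fisher's exact test at 0.05) reproduces as 87.0% by exact enumeration and does not depend on the visit windows.

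**Window limits (Table 1).**
- Earliest contact: 60 − 7 = day 53.
- Latest contact: 60 + 7 = day 67.
- Permitted days: 67 − 53 + 1 = 15, of which days 53 to 59 (7 of 15) fall before the endpoint closes.

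**Days left unobserved.** For a contact on day d the shortfall is max(0, 60 − d).
- Worst case, d = 53: 7 days. Against the full horizon this is 7/60 = 11.7%.
- Evenly spread contacts over days 53 to 67 (assumed; the protocol does not say how contacts will fall): (7 + 6 + 5 + 4 + 3 + 2 + 1)/15 = 28/15 = 1.87 days, and 1.87/60 = 3.1%.

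**What this could mean in deaths.** The protocol gives no 60-day mortality, so this is an illustration over a range. Assume a constant hazard h = −ln(1 − m)/60 for true 60-day mortality m. A contact on day 53 then misses exp(−53h) − exp(−60h):

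| Assumed 60-day mortality | Missed if contacted on day 53 |
|---|---|
| 5% | 0.6 percentage points |
| 10% | 1.1 |
| 20% | 2.1 |
| 30% | 3.0 |

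That is about 10 to 11% of the deaths, in the worst case and if no other route reports them. If deaths cluster early in the outbreak the share is smaller; if the outbreak is still running it may be larger.

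**The sections side by side.** Section 6.4 fixes the horizon at day 60. Section 14.1.2 promises monitoring for 60 days. Section 14.3 stops capture at the final visit, which Table 1 allows on day 53. All three can be met only when the contact falls on or after day 60.

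**The case against.** The best reply is that the day-60 contact is not the only route. Death and hospitalization are serious adverse events by definition, Section 14.1.2 monitors these for 60 days, and Section 14.2 requires prompt reporting once the site knows. In a unit whose outbreak has not been declared over, the line lists described in Section 13.4 may also run past day 40. This stands in part: a death on day 57 may well be reported. But the 24-hour duty starts only when the site becomes aware and requires no further inquiry, and Section 14.3 can be read as ending capture with an early final visit. The gap is narrowed, not clearly closed.

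Symmetric windows are also ordinary operational tolerances, and the time-to-event models in Section 15.3.2 could censor at the contact date. That would help those models. It would not complete the proportion dead by day 60, which needs status on day 60. The late half of the window does no harm to the mortality outcome, provided dates of death are recorded.

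A reader might infer more than the documents support:
- **That the ±4-day window closes day-40 outcomes early in the same way.** For symptomatic resident infections, deaths and transfers it does not. Home staff report these daily and charts are reviewed. Section 12.2.1 expects anyone meeting the case definition to be tested, and the later contact asks again about deaths and case counts. Infections found only by the scheduled swab do depend on its date. Scoring swabs from days 40 to 44 as day-40 status is no remedy, because it would count infections arising after an endpoint fixed at day 40.
- **That the loss is 35%.** This takes 7 of the 20 days after day 40. The endpoint runs from the start of treatment, so 60 days is the proper denominator.
- **That one arm is favoured.** The windows are the same in both arms, and Section 9.2 states that outcome assessors are blinded.

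**Conclusion.** The point holds for day 60. The only scheduled ascertainment of resident deaths after day 40 may be made up to 7 days before the outcome closes, and the safety sections disagree on whether capture then continues. The shortfall is at most 11.7% of the 60-day horizon, and about 3% on average if contacts are evenly spread, which is an assumption. The share of deaths lost cannot be derived from the protocol; the constant-hazard figures are illustrative and assume that no other route reports those deaths.

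The consequence is under-ascertainment and uneven follow-up in both arms, with no directional bias shown. The primary outcome is not affected. This is a modest defect, worth correcting because the loss is avoidable and cannot be repaired at analysis.

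**What to change.** - In Table 1, replace Day 60±7d with Day 60 to 67 (0/+7).
- In Section 13.6, require the dates of deaths, hospitalizations and serious adverse events, and state that events through day 60 are counted.
- Reconcile Section 14.3 with Section 14.1.2 so that capture of serious adverse events runs through day 60 whatever the date of the last contact.
- Leave the day-40 swab window as it is.

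The change adds no visit, call or swab. Permitted contact days fall from 15 to 8 (days 60 to 67), about half, which is the real cost. The latest permitted contact is still day 67: for a unit whose day 1 is 31 October 2020 that is 5 January 2021, well inside the study period ending 31 March 2021.
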